3.2.2 SECONDARY ENDPOINTS

- The change in square root geographic atrophy (GA) lesion size from baseline to Month 6 as measured by FAF.
- Change in best corrected visual acuity (BCVA).
- Change in low luminance best corrected visual acuity (LL-BCVA).
- Relationship between GA lesion size changes and changes in BCVA.
- Change in vital signs.

- Increase in intraocular pressure (IOP).

Pharmacokinetic (PK) parameters

- Exposure after single dose Fludrocortisone acetate IVT injections.
- Serum maximum observed concentration.
- Time to maximum measured concentration
- Terminal elimination half-life.

4 STUDY POPULATION

The study population includes approximately 9 (n=9) subjects to be enrolled at approximately 1 site. To participate in the study, subjects must be diagnosed with GA of the macula associated with AMD in both eyes. If both eyes meet the criteria and qualify for the study, the eye with the best visual acuity at the screening visit will be designated as the study eye. If both eyes have the same visual acuity, the right eye will be used as the study eye.

The complete inclusion and exclusion criteria are presented in the Synopsis, Section 1.

4.1 WOMEN OF CHILDBEARING POTENTIAL

WOCBP are defined as pre-menopausal women physiologically capable of becoming pregnant.

4.2 WOMEN OF NON-CHILDBEARING POTENTIAL

WONCBP are defined as women meeting any of the following criteria:

- Older than 45 years with amenorrhea for > 2 years or older than 60 years with amenorrhea for > 1 year. Both confirmed by FSH and LH levels.
- Has undergone hysterectomy,
- Has undergone bilateral oophorectomy,
- Has undergone bilateral salpingectomy

4.3 APPROVED METHODS OF CONTRACEPTION

Approved methods of contraception include: oral contraceptives, intrauterine device, medically acceptable barrier methods (i.e. condom), implantable or injectable contraceptives or removable birth control device. Subjects practicing abstinence and coitus interruptus (pull out method) must agree to use an approved method of contraception during the study

5 TREATMENT OF SUBJECTS

5.1 ALLOCATION OF TREATMENT

Each subject will be assigned a unique screening number before screening. Subjects who complete the study screening assessments and meet all the eligibility criteria will be scheduled to enter the study and will receive treatment with intravitreal Fludrocortisone acetate on Day 0.

5.2 TREATMENTS ADMINISTERED

5.2.1 DOSE LEVELS AND STUDY ARMS

A single dose of 1- and 2 mg Fludrocortisone acetate/0.1mL will be tested in this study. Subjects will receive 1 IVT injection as outlined in the table below.

	Treatment Arm	Dose Escalation
Part 1	Fludrocortisone acetate 1 mg/0.1mL at Day 0	If no dose limiting toxicity is observed in 3 patients at this given dose level, the dose will be escalated to the following level:
Part 2	Fludrocortisone acetate 2 mg/0.1mL at Day 0	

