1.1 SYNOPSIS

Title:	A Phase 1b, study of safety and tolerability of Intravitreal Fludrocortisone acetate (FCA in Patients with Geographic Atrophy (GA)
Sponsor:	Eye Co Pty Ltd
Protocol Number, Version and Date:	EC-FCA-001/ Version 1.3 / 22 January 2020
Investigational Product, Dose and Route of Administration:	Fludrocortisone acetate (FCA) 1mg/0.1ml & 2mg/0.1ml Intravitreal (IVT) injection
Rationale for dose:	
Single dose of 0.1 ml in a concentration of 1mg/0.1 mL and 2mg/0.1mL was selected based on previous pre-clinical model (Kivilcim et al). There were no signs of retinal toxicity on slit-lamp examination, indirect ophthalmoscopy, or by light microscopy in all eyes injected with 400µg/0.1mL, 1mg/0.1mL and 2mg/0.1mL. However, it was reported 1 case of intravitreal haemorrhage in 4 mg/0.1 mL.
 
Systemic injection of Fludrocortisone acetate has serious mineral corticoid and glucocorticoid side effects such as hypertension, potassium loss, Cushingoid changes, etc. Intravitreal injection fludrocortisone acetate may avoid systemic side effects.

Objectives:	To determine safety and tolerability of a single dose intravitreal (IVT) injection of 1mg/0.1mL and 2mg/0.1mL FCA in subjects

with GA secondary to Age-Related Macular Degeneration (AMD).

Study Population: Study population will comprise of patients with GA secondary to AMD in both eyes with no previous treatment. The study is planned to enrol up to 9 participants.

Study Design: This study is planned to enrol 9 participants to assess dose escalation based on a 3+3 algorithm. Enrolment will stop if > 2 patients experience dose-limiting toxicity at any time during the study. Dose-limiting toxicity is defined by intraocular inflammation, elevated IOP, reduced vision (loss of ≥ 15 letters), or haemorrhage within 28 days after injection.

Part 1 involves a single participant to assess safety and tolerability of 1mg/0.1mL FCA. This participant will be followed for up to 28 days and reviewed by a safety review committee prior to the recruitment of a further 2 participants treated with 1mg/0.1mL FCA totalling in 3 participants in the first cohort.

Part 2 involves a single participant to assess safety and tolerability of 2mg/0.1mL FCA. This participant will be followed for up to 28 days and reviewed by an independent safety review committee prior to the recruitment of a further 5 participants treated with 2mg/0.1mL FCA totalling in 6 participants in the second cohort.

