6.2 SUBJECT ENROLLMENT

It is the responsibility of the investigator to ensure that subjects are eligible to participate in the study prior to enrollment and throughout the study. Documentation of the personally signed and dated informed consent of each subject, using the study-specific ICF, is required before initiating the Screening process. After written informed consent has been obtained and eligibility to participate established, investigative site personnel will obtain the subject's identification number. Only eligible subjects will be allocated to the open label FCA 1 mg/0.1mL or 2mg/0.1 mL.

Enrollment will occur in two parts in order to minimise the likelihood that subjects will be exposed to risks. During part 1 & 2, subjects will be screened one by one as only one patient will initially be enrolled during part 1 of the trial. The first enrolled subject will participate in a screening period of up to 14 days and a follow-up period of 28 days, to detect an IOP response.

After first subject has completed the follow-up of 28 days after FCA 1mg/0.1 mL injection, The subject's safety data will be reviewed the safety data of this will be reviewed by an independent safety review committee to determine whether to commence enrolment of additional 2 patients in the first cohort of 1mg/0.1mL dose of FCA. Enrolment will be stopped if >2 patients experience limiting-toxicity adverse event related to the study drug. If no more than two adverse events considered to be related to the study drug occur with limiting toxicity, the second cohort will be recruited. Dose-limiting toxicity is defined by intraocular inflammation, elevated IOP, reduced vision (loss of ≥ 15 letters), or haemorrhage within 28 days after injection.

Part 2 will take in place if the 3 subjects have tolerated well the dose. Part 2 initially involves a single subject treated with 2mg/0.1mL FCA to assess safety and tolerability. This subject will be followed for up to 28 days and reviewed by an independent safety

review committee prior to the recruitment of a further 5 subjects treated with 2mg/0.1mL FCA totalling in 6 subjects in the second cohort.

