7.11.3.1 WITHDRAWAL

Participants may choose to withdraw from this study for any reason at any time without penalty or prohibition from enrolling in other clinical protocols.

Participant wishing to withdraw from the study completely will be offered an early termination visit.

This early termination visit will include the examinations outlined in Section 6.3.1.

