9.7 DATA SAFETY MONITORING BOARD

An independent DSMB will be convened. The mission of the DSMB will be to ensure the ethical conduct of the trial and to protect the safety interests of patients in this study. The DSMB will be responsible for reviewing the cumulative safety results from the study. The DSMB will meet prior to the commencement of the study, and will review all

available safety/tolerability data (e.g., adverse events, serious adverse events, clinical laboratory assessments, blood pressure, haematology, urology) at Day 0 and 1 month after IVT injection of FCA of the initial participant in Part 1 and 3 (prior to Part 2 & 4 of the study), and convene as required throughout the study period to review data and potential safety risks. The criteria for evaluating study continuation will relate to study safety, including the incidence and severity of ocular and/or systemic side effects not limited to but including; change in IOP of >10mmHg, a loss of 15 letters or more in BCVA, presence or intraocular inflammation, presence or absence of ocular pain, change in BP of 30mmHg (systolic or diastolic), incidence of hospitalisation or systemic illness, and any other ocular or systemic adverse events reported. Any changes will be referenced to baseline measurements. The DSMB will then meet at the conclusion of the study and after the final statistical analysis in order to review all data.

DSMB will consist an ophthalmologist, and a biostatistician, both independent of the study team.

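### The step from 1 mg to 2 mg is not tied to the protocol's own 28-day DLT window, and the sentinel and DSMB review wording conflicts

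*Protocol*

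**What the plan says.** - **Window.** The synopsis and Protocol Section 6.2 list intraocular inflammation, raised IOP, a loss of at least 15 letters and haemorrhage, closing with "haemorrhage within 28 days after injection". I read the 28 days as applying to all four.
- **Escalation from 1 mg to 2 mg.** The table in Section 5.2.1 escalates "If no dose limiting toxicity is observed in 3 patients at this given dose level". Section 6.2 says "Part 2 will take in place if the 3 subjects have tolerated well the dose". The guidance in Sections 6.2 and 8.3 treats a dose as tolerated when no clinically important drug-related event or laboratory abnormality occurs. It sets no minimum observation time.
- **Expansion at 1 mg.** Section 6.2 allows two more patients, after committee review, "After first subject has completed the follow-up of 28 days after FCA 1mg/0.1 mL injection". The synopsis says of the same patient: "This participant will be followed for up to 28 days".
- **Expansion at 2 mg.** Section 6.2 says of the first 2 mg patient: "This subject will be followed for up to 28 days". An independent committee then reviews before five more are recruited. The synopsis agrees.
- **DSMB.** Section 9.7 schedules reviews at Day 0 and one month after the injection of the "initial participant in Part 1 and 3 (prior to Part 2 & 4 of the study", and otherwise as required.
- **Leavers.** Section 7.11.3.1 says "Participants may choose to withdraw from this study for any reason at any time", and Section 6.4 classes loss to follow-up as withdrawal. Neither says what this does to the DLT count. Section 8.1 defines a safety population of everyone dosed, and no DLT-evaluable set.

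**The concern.** A toxicity defined over a window can only be declared absent once the window has closed. The protocol makes that link explicit for one person, the first 1 mg patient. For the decision that carries more risk, the move to the higher dose, the link is missing.

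Two things follow from the literal text. First, even if nobody leaves, the second and third 1 mg patients may still be inside their 28 days when the first 2 mg injection is given. Second, if one of the three leaves early without an event, the decision-makers have no rule telling them whether they hold evidence on three patients or on two.

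Section 2.3.3 says the drug has not been used intravitreally in humans and names the two-part design, starting with a single individual, as the way that risk is limited. This governs who is dosed and when, so it must be settled in the protocol and cannot wait for the analysis stage.

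**Working it through.** **1. The plan's own number.** The synopsis gives 3 patients at 1 mg and 6 at 2 mg: 3 + 6 = 9, which reproduces. There is no spare place in that total. Section 8.6 says up to 12, which does not equal 9 and is not explained as an allowance for leavers.

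**2. Each decision against the 28-day window.**

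| Decision | Completed 28 days required? | Review before the decision |
|---|---|---|
| 1 mg: 1 to 3 patients | Section 6.2 yes; synopsis only up to 28 days | Safety review committee, first patient |
| 1 mg to 2 mg | Not stated for patients 2 and 3 | None expressly scheduled for the full cohort |
| 2 mg: 1 to 6 patients | Only up to 28 days, in both places | Independent committee, first patient |

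**3. The DSMB labels.** The study has Parts 1 and 2 only (synopsis, Sections 5.2.1 and 6.2). Read literally, the Section 9.7 review before Part 2 concerns one 1 mg patient. If the labels come from a four-step numbering (1 mg first patient, 1 mg expansion, 2 mg first patient, 2 mg expansion), they match the two first-patient reviews in Section 6.2. Neither reading requires that the second and third 1 mg patients have completed 28 days.

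**4. How much can be unobserved.** Suppose the 2 mg decision is taken when patients 2 and 3 have just had their Day 7 visits. Observed time is 28 + 7 + 7 = 42 of 3 × 28 = 84 patient-days, or half. The literal wording permits this.

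**5. Illustration of an early leaver.** The protocol gives no DLT rate and no dropout rate, so both are assumed. With a true 28-day DLT rate p and k patients fully observed, P(no DLT seen) = (1 − p)^k. Using k = 2 for a cohort of three assumes that the third patient's DLT would arise after leaving, and that this patient is nevertheless counted.

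| p | 3 observed | 2 observed |
|---|---|---|
| 0.10 | 0.729 | 0.810 |
| 0.20 | 0.512 | 0.640 |
| 0.30 | 0.343 | 0.490 |
| 0.50 | 0.125 | 0.250 |

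The one-sided 95% upper limit on the DLT rate after no events is 1 − 0.05^(1/k): 63% for 0 of 3 and 78% for 0 of 2.

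**6. The same effect averaged over the chance of leaving.** Let each patient leave before any DLT can show with probability d. Then P(no DLT seen) = (1 − p(1 − d))³. At p = 0.30:
- d = 5%: 0.715³ = 0.366
- d = 10%: 0.73³ = 0.389
- d = 20%: 0.76³ = 0.439

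These compare with 0.343 when all three are observed. If half of a leaver's risk is seen before departure, d = 10% gives (1 − 0.30 × 0.95)³ = 0.366. The chance of at least one leaver among three is 1 − (1 − d)³: 14%, 27% and 49%.

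**7. Time.** Three successive windows (first 1 mg patient; patients 2 and 3, if dosed together; first 2 mg patient) take 3 × 28 = 84 days. Adding a full 14-day screening period before each gives 84 + 42 = 126 days, within the stated six months of recruitment.

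**The case against.** The best defence is that Section 5.2.1 speaks of toxicity being observed, which can fairly be read as observed over the defined window. The phrase about following up to 28 days looks like loose drafting, because the synopsis applies it to the first 1 mg patient, for whom Section 6.2 requires completion. Visits on Days 1, 7, 14 and 28 include acuity, IOP and slit-lamp examination. Leavers are offered a termination visit, missed visits trigger contact attempts, and the DSMB sees cumulative data and can meet when needed. Under a four-step numbering, its Day 0 review could also fall at the start of 2 mg dosing. Safety is expressly called a medical judgment, so a committee could wait.

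Much of this stands, and it rules out several stronger readings that a reader might infer:
- That early leavers are not replaced, or count as free of DLT. The protocol states neither; it is silent.
- That decisions rest on dosing alone. The 1 mg expansion requires completed follow-up in Section 6.2.
- That the first 2 mg patient is never reviewed. The synopsis and Section 6.2 both provide that review.
- That the higher dose was deliberately given a looser rule. The documents show inconsistent wording, not intent.
- That leavers are the patients most likely to have had trouble. Nothing in the protocol bears on this.

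What the defence does not supply is any sentence that makes the 2 mg decision wait for, or review, the full window in patients 2 and 3. A committee may wait, but nothing obliges it to.

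**Conclusion.** The point holds as a failure to connect the escalation decision to the DLT window, together with two wording conflicts: completed against up to 28 days, and Part labels that do not exist. Followed literally, the protocol allows 2 mg dosing before its own window has closed for two of the three 1 mg patients, without an expressly scheduled review of that complete cohort. That part needs no assumption about rates.

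The size of the early-leaver effect does rest on assumptions. At an assumed 30% DLT rate, the chance of seeing no DLT rises from 34% to 49% if one patient certainly leaves and the DLT would come afterwards. That is a worst case; with a 10% chance of leaving per patient it rises only to 37–39%.

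A separate conflict, between no DLT in Section 5.2.1 and enrolment stopping only above two patients in Section 6.2, may matter more: under the latter, three fully observed patients pass with probability 1 − 0.30³ = 0.973 at the same rate. It also needs reconciling but is not the subject here.

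**What to change.** Reconcile the synopsis and Sections 5.2.1, 6.2 and 9.7:

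1. Make each escalation and expansion decision refer to the 28-day DLT window the protocol already defines, and say what observation of the second and third 1 mg patients the 2 mg decision rests on.
2. State how a patient who leaves before Day 28 counts in that decision. Whether leavers are replaced is for the sponsor to decide; the answer must agree with the planned number (9 in the synopsis, up to 12 in Section 8.6).
3. Use one wording for the follow-up of both first patients, in the synopsis and Section 6.2.
4. Rewrite the DSMB review points in terms of Parts 1 and 2 and the decision points in Section 6.2, and say which body reviews what before 2 mg begins.

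This adds no assessment, since a Day 28 visit is already scheduled. The cost is an amendment of wording and a possible delay of some weeks before 2 mg starts, which fits the six-month recruitment period on the timing above. If the sponsor chooses to replace leavers, each one adds a patient.

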5.2.2 DRUG SUPPLIES

5.2.2.1 IDENTITY OF INVESTIGATIONAL PRODUCT

Fludrocortisone acetate is formulated for intravitreal administration as a 20mg powder for solution for injection.

Each vial contains 10mg of fludrocortisone powder. The diluent consists of Carboxymethylcellulose (0.6%), Polysorbate 80 (0.02%) and Sodium Chloride solution (0.9%) quantity sufficient to 100%. The fludrocortisone powder for solution for intravitreal injection is reconstituted with 1.0ml and 0.5ml diluent for injection dependent upon concentration required. Following reconstitution, the concentration is suitable for delivering at a 1mg/0.1ml or 2mg/0.1ml dose in 0.1 ml intravitreal injection volume.

The fludrocortisone acetate 10mg powder for solution and diluent is for single use and must be stored at 2-8°C, protected from light.

5.2.2.2 ACCOUNTABILITY

IVT Fludrocortisone acetate drug product will be provided to a designee at the study site and must be stored in a pharmacy or otherwise locked and secured, at temperatures between 2°C and 8°C in a refrigerated area with limited, controlled access and temperature monitoring; do not freeze. IVT Fludrocortisone acetate drug should be protected from light by storing in the carton provided. The drug product supply is accessible only to those individuals authorized by the PI. The Sponsor will supply sufficient quantities of Fludrocortisone acetate drug product to allow completion of this study.

Designated study staff will provide the study treatments to the subjects in accordance with their assigned subject numbers and the randomization schedule. During the study, the receipt of the drugs supplied at the clinical site and of study treatment dispensation for each subject will be documented in drug accountability records. These drug accountability records are to be kept separate from the patient medical records and other source documents.

All used vials should be retained by the clinical site until drug accountability monitoring is performed and then returned to the Sponsor or designee, or destroyed per Sponsor instructions.

At the conclusion of the study, any unused investigational product will be retained by the clinical site, returned to the Sponsor or designee, or destroyed per Sponsor instructions, and this will be documented in the drug accountability records.

5.2.3 INTRAVITREAL FLUDROCORTISONE ACETATE ADMINISTRATION

Subjects receiving active treatment will be administered a 1mg/0.1ml or 2mg/0.1mL IVT injection of Fludrocortisone acetate using a 27G thin wall needle, at the discretion of the PI.

Clinic staff involved in the injection tray assembly, anaesthetic preparation, and study drug preparation and administration will follow appropriate aseptic techniques to minimize the risk of potential adverse events associated with IVT injections (e.g. endophthalmitis).

The investigation drug will be presented in a kit containing 1 x 1 ml syringe with 27g 12 mm needle, 1 x 5 ml vial containing sterile fludrocortisone 10mg, 1 x Vial containing 2 ml Diluent for reconstitution and alcohol swab to swab top of vials before puncturing bungs.

- Preparation of the solution

The injecting doctor will withdraw 1.0ml or 0.5ml of diluent and reconstitute the powder. The doctor will then draw up 0.1 ml of the fluid ready for injection.

To minimize IOP elevation after IVT injection of Fludrocortisone acetate, decompression of the eye must be performed before all Fludrocortisone acetate injections. This is done by applying moderate pressure to the globe with cotton swabs for 30-60 seconds during aesthetic preparation.

In addition to the procedures outlined in this protocol, adherence to specific institutional policies associated with IVT injections will be observed.

5.3 CONCOMITANT THERAPIES

Any concomitant medications a participant is receiving at the start of the study or that are given for any reason during the study (except for routine medications given for

ocular procedures required by the protocol, such as topical aesthetic) must be recorded in the source document and CRF including start and stop date and time, dose, route, and indication. In addition, all ocular and non-ocular procedures such as surgical procedures (excluding study treatment procedures) must also be recorded in the source document including start and stop dates. Surgical anaesthetics, paramedical or alternative therapies (e.g. acupuncture, massage) should also be recorded in the source documents and CRF. Metoclopramide or other agents to prevent nausea induced by fluorescein injection may be administered at the discretion of the PI.

5.3.1 ENDOPHTHALMITIS TREATMENT

The decision to treat a participant for endophthalmitis or suspected endophthalmitis will be guided by the clinical judgment of the PI. The treatment method (pars plana vitrectomy vs. vitreous tap) and choice of antimicrobial agents are also at the discretion of the PI and should follow current standard practice patterns. The decision to use IVT steroids (e.g. dexamethasone) for the treatment of endophthalmitis is also at the discretion of the PI.

6 STUDY PROCEDURES

6.1 STUDY DESIGN

This is a Phase 1b study to assess the safety and tolerability of a single dose of IVT injection of Fludrocortisone acetate in subjects with GA associated with Age-Related Macular Degeneration.

Patients diagnosed with GA associated with age-related macular degeneration in the study eye and who meet all inclusion/exclusion criteria will be included in the study.

The study is planned to enroll an initial cohort of 3 patients in a dose of 1mg/0.1mL. A total of 9 participants can be included to assess dose escalation based on 3+3 algorithm.

Patients should be screened up to 14 days before receiving Fludrocortisone acetate. Upon entry into the study, patients will be assigned a subject screening number. Subjects who meet all inclusion and exclusion criteria and are confirmed as eligible by the CRC will return to the clinic for the administration of single dose IVT Fludrocortisone acetate (Day 0) as outlined in Section 7.1.

All subjects will return to the clinical site on Day 1 and Day 7 to assess acute safety after the injection. After that, all subjects will return for another 6 follow-up visits and 6 months after the injection. See Study Outline below.

Safety will be assessed throughout the study; serial blood samples and urine samples will be collected. Blood samples will also be collected for the PK assessment of Fludrocortisone acetate.

The planned length of participation in the study for each subject is approximately 6 months (from Day 0 – through completion of the Month 6 (Day 150) follow-up procedures).

The study is planned to take place over approximately 12 months (from screening of the first subject through completion of the last subject's exit visit).

